### **Dosimetry**

Previously, for the antibody trastuzumab, it has been shown that when giving a pre-dose of cold (i.e. not radiolabeled) trastuzumab, prior to giving the radiopharmaceutical, the toxicity to the liver (and other organs) was found to be significantly lower resulting in the ability to go up on the dose of the radiopharmaceutical given, improving the preoperative image quality. For Zr-panitumumab, there is little data on dosimetry. At the moment one publication reporting on data in 3 patients (28) whereby it was shown that upon giving a ~1 mCi dose, there's relative high toxicity to the organs, in particular the liver (28).

In our current study, in a subset of 3-5 subjects we will collect dosimetry data by assessing the biodistribution of Zr-panitumumab over time as such to determine the toxicity of Zr-panitumumab to the organs. To obtain dosimetry data, at various time points after injection of Zr-panitumumab, PET/CT scans are to be acquired. The minimum number of PET/CT scans needed is three.

For the current study, these three PET/CT scans will be obtained between the end of observation period after the Zr-panitumumab infusion on Day 0 and the day before surgery (inclusive). If available, the scans will be performed on Day 0, Day 1 and on the day before surgery.

For each patient, on the acquired PET/CT scans, volumes of interest (VOIs) will be drawn around the organs, tumor and lymph nodes. Subsequently, the total activity in each VOI will be recorded in units of Becquerel (Bq). Time activity curves (TACs) will be generated and then integrated to obtain the number of disintegrations (NDs) in each region. Hereafter the data will be loaded into dedicated software (e.g., OLINDA/EXM code (version 1.1.) after which the absorbed dose (in mGy/MBq) to each VOI can be determined. The internal dosimetry calculation model will be implemented following the Committee on Medical Internal Radiation Dose (MIRD) guidelines.

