**Table 1: Dosing Schedule**

No. of subjects	14
Dose of panitumumab-IRDye800	30 mg
Dose of Zr-panitumumab	1.0 mCi, allowable range 0.8 to 1.2 (29 to 44 Mbq)
Specific Activity of Zr-panitumumab	>200 Ci/mmol
PET imaging post-infusion*	Day 0 to the Day before Surgery
Timing of surgical procedure post-infusion	Day 2 to 5 post-infusion

Each subject will be followed for 30 days following the last dose of study medication.

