## **4. TREATMENT PLAN**

### **4.1 Treatment Schedule**

This study will assess a microdose of Zr-panitumumab and an imaging dose of panitumumab-IRDye800 in 14 subjects. The study drugs will be administered on Day 0, and subjects will undergo one Zr-panitumumab PET/CT imaging anytime starting on Day 0 and the Day before Surgery (inclusive).

Subjects enrolled in the dosimetry sub-study will undergo imaging anytime starting on Day 0 and until the day before surgery (inclusive), for a total of three scans; if available, the scans will be performed on Day 0, Day 1 and on the day before surgery.

Subjects will undergo surgical resection at 2 to 5 days after infusion of study drug (see Table 1). Intraoperative and post-operative imaging data will be collected to answer the study objectives. The study will be stopped if any 2 subjects experience a DLT of grade 2 or higher that is likely to be related to the study drugs administered.

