**Rationale for observation period.** We will follow up with subjects on Day 15, which is greater than 4 half-lives of panitumumab. The half-life of panitumumab when given in multiple doses is known to be approximately 7 days (per package insert). However, when administered at smaller doses the half-life is less since the pharmacokinetics are non-linear. We know that at 2 mg/kg, the half-life is 2.3 days (FDA Drug Approval Package, Clinical Pharmacology Biopharmaceutics Review, application 125147), which is less than the 1 mg we are administering as our highest dose. Because the highest proposed dose in the current study is 50 mg of panitumumab-IRDye800, it is not expected to be detectable beyond 12 days after administration in our subject population. Fifteen days is also greater than 4-fold the half-life of Zr, which is 78.4 hours (3.3 days). The duration of 15 days after infusion is therefore chosen as the time point to assess for safety. The study will also follow up with subjects on Day 30.

**Pharmacokinetic intervals.** Because the pharmacokinetics of single dose of panitumumab are well known, only limited pharmacokinetics will be performed. Blood levels will be monitored on Day 0 before infusion; 1 to 2 hours after infusion; and on the day of surgery, and on Day 15 for panitumumab-IRDye800 and free IRDye800. Clearance of panitumumab occurs through the binding in the liver and through the reticuloendothelial system as occurs with endogenous immunoglobulin.

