6. A serum pregnancy test will be obtained on all women of childbearing age at baseline; a urine pregnancy test will be performed on Day 0 if the result of a serum pregnancy test within 72 hours before administration of panitumumab-IRDye800 is not available.
7. Blood samples for serum level of panitumumab-IRDye800 antibody and unconjugated dye, and  $^{89}\text{Zr}$ -panitumumab antibody will be drawn as follows: on Day 0 prior to panitumumab-IRDye800 infusion and at the end of the 1-hour ( $\pm 10$  mins) observation period after completion of injection of  $^{89}\text{Zr}$ -panitumumab; on Day 1-4 (only one sample will be collected on the same day when the PET/CT will be performed); on Day of surgery and on Day 15. The Day 15 time point will be 15 days  $\pm$  4 days, but is abbreviated as Day 15 throughout the protocol.
8. Blood will be collected on Day 0 prior to panitumumab-IRDye800 dose and on Day 15 and banked for future immunogenicity testing. Immunogenicity testing time points will not vary with dose.
9. Panitumumab-IRDye800 infusion to be given over 15 ( $\pm 5$  mins) minutes followed by 30 minutes ( $\pm 10$  mins) observation period.
10.  $^{89}\text{Zr}$ -panitumumab administered as a bolus injection to be done after the end of the observation period after panitumumab-IRDye800 infusion; will be followed by 1 hour ( $\pm 10$  mins) of observation period.
11. Surgical excision will be performed 2-5 days after the infusion of the study drugs.
12. A  $^{89}\text{Zr}$ -PET/CT scan will be acquired after injection of  $^{89}\text{Zr}$ -panitumumab. One scan will be performed at any time starting on Day 0 (after end of observation period post  $^{89}\text{Zr}$ -panitumumab administration) and until the day before surgery (inclusive). Subjects enrolled in the dosimetry sub-study will undergo three scans, performed at any time starting on Day 0 (after end of observation period post  $^{89}\text{Zr}$ -panitumumab administration) and until the day before surgery (inclusive); if available, the scans will be performed on Day 0, Day 1 and on the day before surgery.
13. A standard of care  $^{18}\text{F}$ -FDG-PET scan acquired within year from the day of study drug infusion is acceptable, even if this scan was/is acquired outside of Stanford.

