### **9.2.2 Day 0**

- **Prior to Infusion**
  - Vital signs (blood pressure, heart rate, respiratory rate, temperature)
  - Assessment of performance status (within 21 days)
  - Physical examination (within 21 days)
  - Chemistries (electrolytes, creatinine, BUN, magnesium, phosphorus) (within 21 days)
  - Pregnancy test for women of childbearing potential. If the result of a serum pregnancy test within 72 hours before administration of panitumumab-IRDye800 is not available, a urine pregnancy test will be performed on Day 0
  - Blood sample for panitumumab-IRDye800 antibody and Zr-panitumumab antibody
  - Blood sample for future assessment of immunogenicity
- **IV infusion of panitumumab-IRDye800 over 15 minutes (± 5 mins)**
- **Vital signs immediately following panitumumab-IRDye800 infusion (+ 5 mins)**
- **Observation for 30 min (± 10 mins)**
- **ECG 30 min (± 10 mins) after the end of panitumumab-IRDye800 infusion**
- **Vital signs just before Zr-panitumumab administration**
- **IV injection of Zr-panitumumab bolus** followed by:
  - Vital signs immediately following Zr-panitumumab administration (+ 5mins)
  - Observation for 1 hour (± 10 mins)
  - Blood sample for panitumumab-IRDye800 antibody and Zr-panitumumab antibody collected at 1 hour (± 15 mins) after administration of Zr-panitumumab
  - ECG will be obtained at 1 hour (± 15 mins) after administration of Zr-panitumumab
  - Assessment for adverse events at the end of the 1 hour observation period
- **DOSIMETRY STUDY ONLY:**
  - Zr-panitumumab whole body PET/CT imaging after completion of observation

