### **9.2.3 Day 1 to Day before Surgery:**

- The following assessments will be performed once, at any time between Day 1 and the day before surgery (including on Day 1 and on the day before surgery):
  - Blood sample for panitumumab-IRDye800 antibody and Zr-panitumumab antibody.
  - Zr-panitumumab whole body PET/CT imaging.

- Assessment for adverse events.
- Assessment for concomitant medications.
- Imaging using the optical and radiotracer imaging/detection devices in the clinic to assess fluorescence and radiotracer intensity if tumor amenable to imaging and depending on subject availability.
- DOSIMETRY STUDY ONLY:
  - A total of two Zr-panitumumab whole body PET/CT scans will be performed at any time between Day 1 and the day before surgery (including on Day 1 and on the day before surgery if possible); if available, the scans will preferably be performed on Day 1 and on the day before surgery.
  - Blood sample for panitumumab-IRDye800 antibody and Zr-panitumumab antibody will be collected on the same days when PET/CT imaging is performed.

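### Minor, exploratory only: the dosimetry sub-study does not exclude subjects with Day 2 surgery, and for them no scan informs organ clearance after Day 1

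*Combined protocol and SAP*

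**What the plan says.** Section 2.4 (Dosimetry) plans to measure biodistribution over time in 3-5 subjects, integrate a time-activity curve for each region, and convert the result to absorbed dose. On the number of scans it states: "The minimum number of PET/CT scans needed is three". On timing, it places the scans between the end of Day 0 observation and the day before surgery, inclusive, and adds a preference: "If available, the scans will be performed on Day 0, Day 1 and on the day before surgery".

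The surgery window is "Day 2 to 5 post-infusion" (Table 1), and Section 4.1 says the same: "Subjects will undergo surgical resection at 2 to 5 days after infusion of study drug".

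The visit-level text is more specific about the scans. Section 9.2.2 gives dosimetry subjects one Day 0 scan: "whole body PET/CT imaging after completion of observation". Section 9.2.3 adds two more: "whole body PET/CT scans will be performed at any time between Day 1 and the day before surgery". Table 5, note 12 is looser: "Subjects enrolled in the dosimetry sub-study will undergo three scans, performed at any time starting on Day 0".

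The eligibility criteria (Sections 3.1 and 3.2, Appendix A) and the dosimetry text contain no minimum interval from infusion to surgery for sub-study entry, no minimum gap between scans and no rule for Day 2 surgery. Section 1.3 lists dosimetry as an exploratory objective, to be reported in publications only.

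**The concern.** If surgery is on Day 2, the day before surgery is Day 1. The preferred schedule then names only two different days, and the three required scans become one on Day 0 and two on Day 1. The count of three is met, but the spread over time that makes three scans useful is not.

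The quantity of interest is the integral of activity over all time. For a Day 2 subject, the part after Day 1 rests on a slope estimated from scans close together near the start of the curve. With 3-5 subjects, one such curve is between 1/5 = 20% and 1/3 = 33% of the sub-study data. Section 2.4 describes existing dosimetry data for this agent as scarce, so each curve counts.

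**Working it through.** **1. Scan days by day of surgery.** The last permitted scan day is the surgery day minus 1.

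| Surgery | Last scan day | Distinct days under the stated preference |
|---|---|---|
| Day 2 | Day 1 | 2 (Days 0, 1) |
| Day 3 | Day 2 | 3 (Days 0, 1, 2) |
| Day 4 | Day 3 | 3 (Days 0, 1, 3) |
| Day 5 | Day 4 | 3 (Days 0, 1, 4) |

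Only Day 2 surgery makes three distinct days impossible. For later surgery the preference gives three distinct days but does not require them.

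**2. Share of decays after the last scan, physical decay only.** The half-life is 78.4 h (Section 5.1.1). The share after time t is 0.5^(t/78.4):
- 24 h: 0.809
- 48 h: 0.654
- 72 h: 0.529
- 96 h: 0.428

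**3. Adding biological clearance.** Section 4.3 gives two antibody half-lives: about 7 days with multiple doses and, at a lower dose, "We know that at 2 mg/kg, the half-life is 2.3 days". The effective half-life is 1/(1/78.4 + 1/(24b)), with b in days.
- b = 2.3: 1/(1/78.4 + 1/55.2) = 32.4 h
- b = 7: 1/(1/78.4 + 1/168) = 53.5 h

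| Last scan | Share after, 32.4 h | Share after, 53.5 h |
|---|---|---|
| 24 h | 0.598 | 0.733 |
| 48 h | 0.358 | 0.537 |
| 72 h | 0.214 | 0.393 |
| 96 h | 0.128 | 0.288 |

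**4. Precision of the integral (illustration only).** Assumptions, none of them in the documents: mono-exponential organ clearance, independent 5% error per scan, first scan at 2 h, and a last Day 1 scan somewhere from 26 to 36 h. Fit log activity = a − λt by least squares. The integral is exp(a)/λ. By the delta method the standard error of its log is

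SE = 0.05 × √[1/3 + (τ − m)²/S],

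where τ = T/ln 2, T is the effective half-life, m is the mean scan time and S is the sum of squared deviations of the scan times. τ is 46.7 h for T = 32.4 h and 77.2 h for T = 53.5 h.

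| Scans (h) | m | S | SE, T = 32.4 h | SE, T = 53.5 h |
|---|---|---|---|---|
| 2, 22, 26 (Day 2 surgery) | 16.7 | 330.7 | 8.8% | 16.9% |
| 2, 24, 30 (Day 2 surgery) | 18.7 | 434.7 | 7.3% | 14.3% |
| 2, 24, 36 (Day 2 surgery) | 20.7 | 594.7 | 6.1% | 11.9% |
| 2, 24, 48 (Day 3 surgery) | 24.7 | 1058.7 | 4.5% | 8.6% |

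For the first row at T = 32.4 h: (46.7 − 16.7)² / 330.7 = 2.74, and 0.05 × √(0.333 + 2.74) = 0.088. An assumed 10% scan error would double every SE.

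**The case against.** - **Conditional.** The gap appears only if a Day 2 subject is chosen for one of 3-5 places among 14. Surgery is already planned at entry, so the team can see the date and may avoid this. The documents do not give the distribution of surgery days, so the frequency is unknown. This stands: the plan permits the poor schedule but does not prescribe it.
- **The longer half-life is doubtful here.** Section 4.3 gives 7 days for multiple doses and says the half-life is shorter at smaller doses. The 30 mg dose is about 0.41 mg/kg, below the 2 mg/kg behind the 2.3-day figure. The 32 h column is therefore the more relevant one for serum. Organ retention may differ, and the documents give no organ half-life.
- **The model does not fit every region.** Section 4.3 describes tumor accumulation over the first 24 to 36 hours and fluorescence rising up to 3 days. Step 4 says nothing about regions still taking up tracer.
- **Later blood samples exist.** Table 5, note 7 has samples on the day of surgery and Day 15. They inform blood clearance after Day 1, but not the organ activity that is integrated.
- **A looser window.** The synopsis figure footnote runs to the day of surgery. Sections 2.4, 4.1 and 9.2.3 and Table 5 all stop at the day before.
- **A matter of degree.** Day 5 surgery still leaves 43% of physical decays after a 96 h scan, and no precision target is set. This stands: the change removes only the worst case.

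A reader might go further and infer that Day 2 subjects could have two scans on Day 0. The looser wording of note 12 allows it, but Sections 9.2.2 and 9.2.3 place one scan on Day 0 and two from Day 1. A reader might also take the reproduced Tables 3 and 4 (effective dose 0.264 against 0.330 mSv/MBq, with and without the late scan) as proof of bias. Those tables also differ by one subject, so they are at most suggestive.

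**Conclusion.** The point holds as a minor one, confined to an exploratory objective. Following the stated rules with a Day 2 subject leaves no scan to inform organ clearance after Day 1. At least part of the loss is certain: 81% of physical decays follow a 24 h scan, against 65% at 48 h. The loss of precision is illustrative: about 6-9% against 4.5% at a 32 h effective half-life, and 12-17% against 8.6% if organ retention is nearer 53 h. Both rest on the assumed mono-exponential model, 5% scan error and scan hours.

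The documents do not support reading this as a threat to the trial's conclusions or to subject safety. No primary or secondary analysis or stopping rule uses the dosimetry results, and the number of scans is the same either way. Nor does it make the sub-study unusable: a second Day 1 scan still adds information, and Day 3-5 subjects have room for three distinct days.

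**What to change.** In Section 2.4 (Dosimetry) and Section 9.2.3:
- Select the 3-5 sub-study subjects from those whose already planned surgery is on Day 3 or later.
- Require the three scans on three distinct days, with the last on the day before surgery.
- Report the extrapolated fraction of each time-activity integral.

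This takes an eligibility sentence, a scan-spacing sentence and one reporting item. It adds no scan or visit and moves no surgery. The downside is that fewer of the 14 subjects qualify and scheduling is less flexible, so filling the 3-5 places may take longer.

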## **3. PARTICIPANT SELECTION AND ENROLLMENT PROCEDURES**

### **3.1 Inclusion Criteria**

1. Biopsy-confirmed diagnosis of squamous cell carcinoma of the head and neck.
2. Subjects diagnosed with any T stage, any subsite within the head and neck that are scheduled to undergo surgical resection. Subjects with recurrent disease or a new primary will be allowed.
3. Planned standard of care surgery with curative intent for squamous cell carcinoma.
4. Age  $\geq$  19 years.

5. Have acceptable hematologic status, coagulation status, kidney function, and liver function including the following clinical results:

Hemoglobin  $\geq$  9 gm/dL  
White blood cell count  $>$  3000/mm^3  
Platelet count  $\geq$  100,000/mm^3  
Serum creatinine  $\leq$  1.5 times upper reference range

### **3.2 Exclusion Criteria**

1. Myocardial infarction (MI); cerebrovascular accident (CVA); uncontrolled congestive heart failure (CHF); significant liver disease; or unstable angina within 6 months prior to enrollment.
2. Previous bilateral neck dissection.
3. History of infusion reactions to monoclonal antibody therapies.
4. Pregnant or breastfeeding.
5. Magnesium or potassium lower than the normal institutional values.
6. Subjects receiving Class IA (quinidine, procainamide) or Class III (dofetilide, amiodarone, sotalol) antiarrhythmic agents.
7. Subjects with a history or evidence of interstitial pneumonitis or pulmonary fibrosis.
8. Severe renal disease or anuria.
9. Known hypersensitivity to deferoxamine or any of its components.

### **3.3 Informed Consent Process**

All participants must be provided a consent form describing the study with sufficient information for participants to make an informed decision regarding their participation. Participants must sign the IRB approved informed consent prior to participation in any study specific procedure. The participant must receive a copy of the signed and dated consent document. The original signed copy of the consent document must be retained in the medical record or research file.

### **3.4 Enrollment Process**

After signing an informed consent, subjects will be assigned a unique subject identification number based on the OnCore number and sequential numeric code (i.e. ENT0066-001, -002, etc.). The subject identification number will be used on all subject specific Case Report Forms (CRFs) and serious adverse event (SAE) forms. Participant information should be entered into OnCore within 5 business days.

### **3.5 Study Timeline**

#### **Primary Completion:**

The study will reach primary completion 24 months from the time the study opens to accrual.

#### **Study Completion:**

The study will reach study completion 36 months from the time the study opens to accrual.

The anticipated study start date: July 2018

The anticipated study completion date: October 2020

## **4. TREATMENT PLAN**

### **4.1 Treatment Schedule**

This study will assess a microdose of Zr-panitumumab and an imaging dose of panitumumab-IRDye800 in 14 subjects. The study drugs will be administered on Day 0, and subjects will undergo one Zr-panitumumab PET/CT imaging anytime starting on Day 0 and the Day before Surgery (inclusive).

Subjects enrolled in the dosimetry sub-study will undergo imaging anytime starting on Day 0 and until the day before surgery (inclusive), for a total of three scans; if available, the scans will be performed on Day 0, Day 1 and on the day before surgery.

Subjects will undergo surgical resection at 2 to 5 days after infusion of study drug (see Table 1). Intraoperative and post-operative imaging data will be collected to answer the study objectives. The study will be stopped if any 2 subjects experience a DLT of grade 2 or higher that is likely to be related to the study drugs administered.

#### **4.2 Administration of study agents**

##### *Panitumumab-IRDye800*

Administration of panitumumab-IRDye800 will be performed consistent with institutional policy. The solution will be diluted to a total volume of 100 mL with 0.9% sodium chloride injection, USP. Dosage level will be 30 mg panitumumab-IRDye800 (<1/12 of a therapeutic dose of panitumumab). Administration of panitumumab-IRDye800 will occur by IV over 15 minutes followed by a 30-minute observation period. Additional treatment for infusion reactions and electrolyte imbalances will be given as per institutional policy, if needed.

##### *Zr-panitumumab*

After infusion of the panitumumab-IRDye800 the subject will receive the prescribed injection of Zr-panitumumab. Approximately 75 MBq (2 mCi) of Zr will be conjugated with panitumumab antibody. The dosage will be <1 mg Zr-panitumumab (< 1% of a therapeutic dose of panitumumab). The Zr-panitumumab will be systemically injected via IV with a dose of 1 mCi (+/- 20%). Subjects will be observed for 1 hour after administration. Additional treatment for infusion reactions and electrolyte imbalances will be given as per institutional policy, if needed. Staff will be trained to handle the amounts of radioactive material represented by Zr-panitumumab. The appropriate equipment will be used to administer and transport the Zr-panitumumab.

A low-dose CT will be obtained from vertex to toes; this will use 120 kV and dose modulation based on body habitus, ranging 10-105 mA. This will be followed by a static PET emission scan over the same area.

All infusions/injections will be done according to Stanford facilities guidelines. Consistent with the panitumumab package insert, the study drugs Zr-panitumumab and/or panitumumab-IRDye800 will not be mixed with, or administered as an infusion with other medicinal products, nor infused through a peripheral intravenous line or indwelling intravenous catheter.

#### **4.3 Dose Rationale**

[figure not shown]
**Rationale for dose of 1.0 mCi (37 Mbq) of Zr-panitumumab and PET imaging at Day 1 to 2 post-infusion.** The absorbed dose to the liver is relatively high, which limits the dose that can be administered to humans to approximately 1.0 mCi. The human studies reported in the literature have used 1 or 2 mCi and achieved good image quality (27,28).

It is hypothesized that the systemic circulation of the antibody-drug will accumulate specifically within the tumor during the first 24 to 36 hours after infusion based on our preliminary data previously presented. However, we do expect that longer periods of accumulation in the primary tumor (2 to 5 days) will result in non-specific drainage of dye into the regional lymph nodes from non-specific lymphatic drainage from the tumor.

**Rationale for dose of 30 mg panitumumab-IRDye800 without loading dose.** Previously we identified a flat dose of 50 mg of panitumumab-IRDye800 as the optimal dose for intraoperative imaging in HNSCC, but we have recently reviewed data for almost 54 patients who received panitumumab-IRDye800 and have evidence to support lowering the dose to 30 mg:

- 1) We have shown that the tumor-to-background (TBR) ratio is the same for doses in the range 25-50 mg. As can be seen in Figure 2 and Table 2, irrespective of the dose given, a fixed dose or a dose in mg/kg, the varies between 2-3. A dose of 30 mg would translate to a dose of approximately 0.41 mg/kg (assuming a patient weighing 73 kg). At this dose, we also do not expect that the timing is going to be of an issue, something which we did see when giving a lower dose of around 0.3 mg/kg (Figure 3).
- 2) There has been progressive improvement in our understanding of the benefit of the surgical imaging over the past 2 years, and we are now looking at margins in the primary specimen, rather than microscopic disease (29–31);
- 3) In the lymph node data that we recently analyzed, we found a high sensitivity and specificity (84.6% and 94.0%, respectively) for identifying metastatic nodes. Furthermore, we demonstrated that a lower dose reduced the number of false-positives lymph nodes identified. Combined, this data leads us to believe that a lower dose (<0.5 mg/kg) may thus allow for improved metastatic lymph node detection compared to a >0.5 mg/kg dose of panitumumab-IRDye800 (32) (Figure 4);
- 4) The imaging software that we have been using continues to improve, and with this increased sensitivity, allows us to detect lower amounts of drug (both LICOR Biosciences Inc., and Novadaq/Stryker are continuously working on improved imaging devices – we have long-standing collaboration agreements in place);
- 5) As of June 2019 we received our second lot of panitumumab-IRDye800 and we have seen an improved fluorescence signal coming from this lot compared to the previous batch.

With that in mind, we would like to change the dose to 30 mg.

**Figure 2.** a) Correlation between primary tumor mean fluorescence intensity (MFI) and the fixed-dose of panitumumab-IRDye800 administered to the patient; b) Correlation between tumor-to-background ratio (TBR) and the fixed-dose of panitumumab-IRDye800 administered to the patient; c) Correlation between primary tumor MFI and the average dose of panitumumab-IRDye800 administered to the patient; d) Correlation

[figure not shown]
**Table 2.** Comparison of clinical variables for primary tumor MFI and TBRs.

Variable	MFI		TBR	
	Mean	p value	Mean	p value
Dose	High	0.33 **	2.8	N.S.
	Low	0.18	3.1	
Time of infusion-surgery	≤ 2 days	0.30 *	3.1	N.S.
	> 3 days	0.18	2.5	
Unlabeled dose	100 mg	0.27	N.S.	2.7
	0 mg	0.26		3.2
Age	≤ 60 years	0.25	N.S.	3.0
	> 60 years	0.27		2.9
Gender	Male	0.24	N.S.	3.0
	Female	0.30		2.9
Primary site	Tongue	0.32	N.S.	3.6 *
	Other	0.23		2.6
Tumor size	≤ 40 mm	0.27	N.S.	3.0
	> 40 mm	0.25		2.8

[figure not shown]
\*p<0.05; \*\*p<0.01; N.S. = not significant

MFI = mean fluorescence intensity; TBR = tumor-to-background ratio. Adapted from Nishio et al., MIB 2018.

between TBR and the average dose of panitumumab-IRDye800 administered to the patient. Adapted from Nishio et al., MIB 2018.

**Figure 3.** a) Within the weight-based dosing group, no significant difference between primary tumor MFI and TBR was found when looking at the time between infusion and surgery (1-2 days vs. >3 days); b) In the fixed-dosing group, significantly higher primary tumor MFIs were found when the infusion to surgery window was 1-2 days vs. 3 days ( $p<0.05$ ). Adapted from Nishio et al., MIB 2018.

**Figure 4.** Effect of the panitumumab-IRDye800 on the find rate of false-positive lymph nodes. a) Rates of true positive, false positive, false negative and true negative lymph nodes (LNs) over three groups by weight adjusted dose. b) Representative fluorescence images of metastatic and benign lymph nodes for the three dose groups.

TP = true positive (fluorescence positive, histopathologically confirmed metastatic LN); TN = true negative (fluorescence negative, histopathologically benign LN); FP = false positive (fluorescence positive, histopathologically benign LN); FN = false negative (fluorescence negative, histopathologically confirmed metastatic LN).

**Surgical timing 2-5 days post-infusion.** Calculating the TBR over time can be used to identify the optimal day of surgery that will provide the greatest tumor contrast. The proposed time course for imaging and surgery is based on data obtained from our cetuximab-IRDye800 and panitumumab-IRDye800 study, which has demonstrated increasing fluorescence intensity up to 3 days post injection of the antibody-dye conjugate (36). We found that most of our subjects had accessible tumors that could be imaged non-invasively in the clinic over time since oral cavity lesions can be well-visualized as well as cutaneous manifestations. The optimal imaging time point for Zr-panitumumab is nearly identical to that of panitumumab-IRDye800. Thus, we plan to perform the surgery or image for up to 5 days to identify the optimal TBR as shown in our previous study.

**Rationale for observation period.** We will follow up with subjects on Day 15, which is greater than 4 half-lives of panitumumab. The half-life of panitumumab when given in multiple doses is known to be approximately 7 days (per package insert). However, when administered at smaller doses the half-life is less since the pharmacokinetics are non-linear. We know that at 2 mg/kg, the half-life is 2.3 days (FDA Drug Approval Package, Clinical Pharmacology Biopharmaceutics Review, application 125147), which is less than the 1 mg we are administering as our highest dose. Because the highest proposed dose in the current study is 50 mg of panitumumab-IRDye800, it is not expected to be detectable beyond 12 days after administration in our subject population. Fifteen days is also greater than 4-fold the half-life of Zr, which is 78.4 hours (3.3 days). The duration of 15 days after infusion is therefore chosen as the time point to assess for safety. The study will also follow up with subjects on Day 30.

**Pharmacokinetic intervals.** Because the pharmacokinetics of single dose of panitumumab are well known, only limited pharmacokinetics will be performed. Blood levels will be monitored on Day 0 before infusion; 1 to 2 hours after infusion; and on the day of surgery, and on Day 15 for panitumumab-IRDye800 and free IRDye800. Clearance of panitumumab occurs through the binding in the liver and through the reticuloendothelial system as occurs with endogenous immunoglobulin.

